## STUDY PERSONNEL

0 unresolved comment(s)

Do you have study personnel who will be assisting with the research?

After selecting 'Yes' or 'No' you must click the 'Save Study Personnel Information' button. [?](#) Yes  No

**RESEARCH DESCRIPTION****0 unresolved comment(s)**

You may attach a sponsor's protocol pages in the "Additional Information" section and refer to them where necessary in the Research Description. However, each prompt that applies to your study should contain at least a summary paragraph.

**Pro Tips:**

- Save your work often to avoid losing data.
- Use one of the attachment buttons in this section or under the Additional Information section to include supplemental information with your application. During the document upload process, you will be able to provide a brief description of the attachment.

**Background**

Include a brief review of existing literature in the area of your research. You should identify gaps in knowledge that should be addressed and explain how your research will address those gaps or contribute to existing knowledge in this area. For interventional research, search PubMed and ClinicalTrials.gov for duplicative ongoing and completed trials with same condition and intervention(s).

Perinatal opioid use disorder (OUD) is a major health concern in the US with significant impact on mothers, infants, and communities. Our team at University of Kentucky/UK HealthCare (UK) has developed a comprehensive clinical care model for perinatal OUD (known as UK-PATHways) that has demonstrated success in maternal and neonatal outcomes. The overreaching goals of the proposed project are to 1) expand the reach of this successful clinical program, 2) to reduce the impact of perinatal OUD in underserved rural areas of our state, and 3) to compare the relative effectiveness methods of delivery active elements of the PATHways program for rural implementation (local group-support vs. telemedicine). The UK-PATHways program preliminary successes during the first three years are clear: enrolled mothers (n>200) have reduced relapse, increased treatment compliance, and improved neonatal outcomes when compared to non-enrolled OUD mothers. However, at this time UK-PATHways is only available at our main healthcare campus in Lexington, KY. Many eligible patients reside great distances from our clinical home and some current patients travel hours to access this valuable resource. While Medication Assisted Therapy (MAT) has become increasingly available in our region, many of the components of the UK-PATHways program are not readily accessible in rural Central and Eastern Kentucky and the quality of programming with MAT treatment is not standardized in these locations. Furthermore, rural patients continue to face challenges related to stigma of their OUD and transportation difficulties if they desire more comprehensive services. The proposed study will evaluate the introduction of essential components of the UK-PATHways program into rural communities, and identify the optimal intervention strategies for expansion of services and to improve the treatment of OUD for rural patients.

**Objectives**

List your research objectives. Please include a summary of intended research objectives in the box below.

Aim 1.) Conduct a randomized cluster trial using a 'hub and spoke' study design, comparing two delivery modes (local GROUP care vs TELEMEDICINE) for the delivery of a PATHways based patient education curriculum at participating regional sites. Each regional site will be randomized to support one of two study arms: 1) Prenatal group care led by a Perinatal Nurse Facilitator and Peer Support Specialist (GROUP arm); or, 2) Telemedicine consultation provided by a Perinatal nurse educator, substance abuse counselor and/or Peer Support Specialists based at the 'hub' site (TELEMEDICINE arm).

Aim 2.) Evaluate the relative effectiveness of each study arm on primary and secondary maternal and neonatal outcomes as compared to the established PATHways program (UK-PATHways: Hub) at the University of Kentucky.

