## Prisoner Categories

- Category 1: My research involves the study of possible causes, effects, processes of incarceration, and of criminal behavior.** (Processes of incarceration can be interpreted broadly to include substance abuse research, half-way houses, counseling techniques, criminal behavior, etc.)
- Category 2: My research involves the study of prisons as institutional structures, or of prisoners as incarcerated persons.** (This category is usually used fairly narrowly – i.e., looking at prisoner diet, conditions of prison, etc.)
- Category 3: My research involves the study of conditions particularly affecting prisoners as a class.** (This category is rarely used – e.g., vaccine trials, research on hepatitis, social and psychological problems such as alcoholism, drug addiction, sexual assaults. Minimal risk studies should not go under this category.)
- Category 4: My research involves the study of practices, both innovative and accepted, which have the intent and reasonable probability of improving the health or well-being of the subject.** (Rare for research involving placebo or control groups to fall in this category because of the difficulty in justifying improvement of the health or well-being of the subject being given placebo or in a control group.) Note: Contact the Office of Research Integrity at [contact] for more information.
- Epidemiologic Research Involving Prisoners [See also SECTION 3 below]**

Explain the research practices that will be used in this study and how they are intended to improve the health and well-being of the participants:

All enrolled study patients will receive a standardized prenatal education curriculum for OUD in pregnancy. Sites have been randomized to receive group prenatal education ("group" arm) imparted through a nurse facilitator and peer support specialist, or through telemedicine sessions with experts in nursing and substance abuse counseling.

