#### Attachments

#### Subject Recruitment Methods & Advertising

Describe how the study team will identify and recruit subjects. Please consider the following items and provide additional information as needed so that the IRB can follow each step of the recruitment process.

- How will the study team identify potential participants?
- Who will first contact the potential subjects, and how?
- Will you use advertisements? If so, how will you distribute those?
- How and where will the research team meet with potential participants?
- If applicable, describe proposed outreach programs for recruiting women, minorities, or disparate populations.
- How you will minimize undue influence in recruitment?
- Attach copies of all recruiting and advertising materials (emails, verbal scripts, flyers, posts, messages, etc.).

For additional information on recruiting and advertising:

- [IRB Application Instructions - Advertisements](#)
- [PI Guide to Identification and Recruitment of Human Subjects for Research](#)

Participants will be recruited based on the following inclusion criteria: Pregnant women at 6-32 weeks gestational age; History of OUD; Who are receiving MAT and obtaining prenatal care at one of the 12 study sites. Patients will be identified by site research nurse (to be determined), viable pregnancy by ultrasound report will be confirmed and diagnosis of OUD and taking MAT will be confirmed. Patient will then be approached about possible recruitment in study. Each study site will have a contracted study nurse who will be identified, CITI trained and added to the IRB for patient recruitment. Although, not an inclusion or exclusion criteria, we have noted that a substantial proportion of potential study participants are under some type of criminal justice supervision at some point during their study participation. We have added a question to the study screener. Importantly, we will not screen or enroll women who are incarcerated in a detention center, easily identified by clothing worn by inmates and/or under escort or restrained by a guard or handcuffs.

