## **Statistical Analysis Plan NCT03725332**

To begin, continuous variables (gestational age at birth, neonatal weight, infant hospitalization length of stay, etc.) will be summarized with descriptive statistics (n, mean, standard error, first and third quartiles, and minimum and maximum); categorical variables (NAS treatment required, mother-infant dyad status, preterm birth, maternal smoking status, etc.) will be summarized with counts and percentages. To investigate differences in outcomes between treatment arms, a generalized linear mixed model will be performed. Mixed models allow for additional flexibility to control clustering while controlling for covariates such as socioeconomic status, race, age, addiction severity, if needed. Results will be presented with means (standard error) by treatment arm. Note that the primary outcome requires a noninferiority analysis; the secondary outcomes require superiority analysis to identify between-group differences. Mixed model assumptions will be assessed using plots of each outcome, diagnostics, and/or residual plots. If deviations from distributional assumptions are identified, remedial measures will be deployed as needed. In the case that methods assumptions are not satisfied, remedial measures (eg, variable transformations, nonparametric methods) will be employed.

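### Aim 2 promises an effectiveness comparison with a single non-randomised Hub, which this design cannot support; it should be a descriptive benchmark, and the SAP should name the noninferiority contrast and its reference arm

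*Combined protocol and SAP*

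**What the plan says.** Aim 2, under Objectives, is to "Evaluate the relative effectiveness of each study arm on primary and secondary maternal and neonatal outcomes as compared to the established PATHways program", identified there as the Hub at the University of Kentucky. The Background says that "UK-PATHways is only available at our main healthcare campus in Lexington, KY", so the comparator is one site.

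Only regional sites are randomised, to GROUP or TELEMEDICINE, 1:1 within two volume strata of six sites each (Objectives; Study Design). Entry is limited to women "Who are receiving MAT and obtaining prenatal care at one of the 12 study sites" (Subject Recruitment Methods & Advertising), and none of the twelve sites listed under Study Population is in Lexington.

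The SAP's only comparative analysis is this: "To investigate differences in outcomes between treatment arms, a generalized linear mixed model will be performed". Adjustment is optional: "controlling for covariates such as socioeconomic status, race, age, addiction severity, if needed". The SAP adds "Note that the primary outcome requires a noninferiority analysis" but names no reference group, and it does not mention the Hub. The third goal in the Background is "to compare the relative effectiveness methods of delivery active elements of the PATHways program for rural implementation (local group-support vs. telemedicine").

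**The concern.** An aim that speaks of relative effectiveness on primary and secondary outcomes calls for a defined comparator group and an analysis that can attribute a difference to the program. For the Hub, the available text supplies neither. A team following the plan would end with no answer to Aim 2, or with an unadjusted or lightly adjusted difference between trial mothers and one academic site that is then reported as effectiveness.

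The primary outcome is neonatal abstinence syndrome (NAS) diagnosis and treatment requirement. Local scoring and treatment practice could plausibly move it, as could referral setting and calendar period. A Hub difference could reflect any of these rather than how the curriculum was delivered.

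A smaller gap concerns the primary test. A noninferiority test is directional, and the SAP states neither the pair of groups being tested nor which of them is the reference.

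**Working it through.** **No plan figure to reproduce.** The documents give no margin, alpha, power, NAS rate or ICC, so the maximum enrolment of 267 cannot be rederived. The main argument is structural, and the arithmetic only shows its scale.

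**Step 1: the sections side by side.**
- Objectives, Aim 2: each arm against the Hub.
- Objectives, Aim 1, and Study Design: two randomised arms, both made up of regional sites.
- Prisoner Categories: "All enrolled study patients will receive a standardized prenatal education curriculum for OUD in pregnancy", delivered by group or telemedicine. The Hub is neither of these arms.
- Data Collection & Research Materials: collection is assigned to study site staff under the university team's oversight, with no Hub extraction described.
- SAP: differences between treatment arms only.

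**Step 2: what an arm-minus-Hub difference estimates.** Write it as (arm program effect − Hub program effect) + (average regional site effect − Hub site effect). With one Hub, its program and site terms always appear together, so no data from this design can split them. Socioeconomic status, race, age and addiction severity are patient-level. They can reduce measured case-mix differences but cannot identify the Hub's own site term.

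**Step 3: inputs for the illustration.**
- From the documents: 267 mothers, or 133.5 per arm; 12 sites, or 6 per arm, giving m = 267/12 = 22.25 per site.
- Assumed: event rate 0.40, so v = 0.4 × 0.6 = 0.24; Hub n = 200 (the Background reports more than 200 program mothers but does not name them as the Aim 2 cohort); ICC from 0 to 0.10; normal approximation.

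**Step 4: precision if the Hub were exchangeable with the regional sites.**
- Hub contrast half-width = 1.96 × √[ICC·v·(1 + 1/6) + (1 − ICC)·v·(1/200 + 1/133.5)]
- Randomised contrast half-width = 1.96 × √[ICC·v·(2/6) + (1 − ICC)·v·(2/133.5)]

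At ICC 0.02 the Hub contrast is 1.96 × √(0.00560 + 0.00294) = 18.1 points. The randomised contrast is 1.96 × √(0.00160 + 0.00352) = 14.0 points.

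| ICC | Hub contrast (points) | Randomised contrast (points) | Ratio |
|---|---|---|---|
| 0 | 10.7 | 11.7 | 0.91 |
| 0.01 | 14.9 | 12.9 | 1.15 |
| 0.02 | 18.1 | 14.0 | 1.29 |
| 0.05 | 25.4 | 16.9 | 1.51 |
| 0.10 | 34.3 | 20.8 | 1.65 |

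**Step 5: coverage if the Hub has a fixed site offset d.** This does not need exchangeability. Suppose the interval allows for clustering within the arm but has no term for the Hub's site effect:
- SE² = v·[1 + (m − 1)·ICC]/133.5 + v/200
- Coverage = Φ(1.96 − d/SE) − Φ(−1.96 − d/SE)

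At ICC 0.02, SE² = 0.00256 + 0.00120 = 0.00376 and SE = 6.13 points. Coverage is 87% for d = 5 points and 63% for d = 10. At ICC 0.05, SE² = 0.00371 + 0.00120 = 0.00491 and SE = 7.01 points. Coverage is 89% and 70%. The estimate itself is shifted by d at any sample size.

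**The case against.** **A non-randomised benchmark is not an error in itself.** That is right. Asking how regional delivery compares with the established program is reasonable, and the Hub has outcome experience to draw on: the Background reports more than 200 mothers, and the neonates section mentions a reduction in NAS. The problem is the effectiveness label without a cohort or an analysis.

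**The source may be described elsewhere.** This is an ethics application that asks for summaries. The data management plan and grant attachments cannot be seen, so a Hub data source may well exist. That would answer the missing description but not the confounding of site with program.

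**The primary noninferiority test is not against the Hub.** A reader might infer that it is, because Aim 2 is the only aim to mention primary outcomes. The documents do not support that. The SAP models differences between treatment arms and reports results by arm, Aim 1 compares two delivery modes, and the third Background goal names local group support against telemedicine. What stands is narrower: the SAP does not say this for the noninferiority test, and it does not say which arm is the reference.

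**The statement that there is no control group proves little.** It answers a prompt about selecting prisoners and is not evidence about a benchmark cohort.

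**The numbers can be pushed too far.** With unlimited enrolment the half-width ratio would be √[(7/6)/(1/3)] = 1.87, but that is a limit. At 267 mothers it is 1.15 to 1.65 for ICC 0.01 to 0.10, and below 1 at ICC 0. Ignoring clustering within arms gives coverage of 85% and 55% for 5- and 10-point offsets, but the SAP plans to allow for clustering. Some sections count 11 sites, which would change the ratios somewhat.

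**Conclusion.** The point holds for Aim 2. The Hub is a single site outside both the randomisation and the entry sites, no Hub cohort or analysis appears in the available text, and its site effect cannot be separated from its program effect. An effectiveness or noninferiority claim against it is not supported. This conclusion needs no numerical assumption.

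The size is illustrative only, because the event rate, ICCs, Hub number and offsets are all assumed. If the Hub is exchangeable with the regional sites, its contrast is about 1.3, 1.5 and 1.65 times as wide as the randomised one at ICC 0.02, 0.05 and 0.10, and slightly narrower at ICC 0. If it carries a 10-point offset of its own, nominal 95% coverage falls to about 63% at ICC 0.02 and 70% at ICC 0.05.

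It would go too far to say that the trial's main comparison is compromised. GROUP versus TELEMEDICINE is randomised, is the natural reading of the SAP and is unaffected. For that test, what remains open is an explicit statement of the contrast and of the reference arm. The change should be made, but it concerns what the trial may claim rather than how it is run.

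**What to change.** 1. Reword Aim 2 so that the Hub results are a non-randomised descriptive benchmark. State the Hub data source and calendar period, and restrict it to mothers meeting the trial's clinical entry criteria. Report estimates adjusted or unadjusted, and make no noninferiority or causal effectiveness claim.
2. Add a SAP paragraph stating that the confirmatory analysis, including the primary noninferiority test, is the randomised GROUP versus TELEMEDICINE contrast. The sponsor should confirm this and name which arm is the reference. Naming the contrast alone leaves the direction of the test open.

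The cost is a reworded aim and one SAP paragraph, with no change to enrolment. The funder may need to agree to the reworded aim. The trial also gives up a stronger statement about matching the Hub, which the design could not have supported. If the sponsor did intend the Hub as the noninferiority reference, the primary analysis would have to be restated.

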**Study Design**

Describe and explain the study design (e.g., observational, secondary analysis, single/double blind, parallel, crossover, deception, etc.).

- *Clinical Research:* Indicate whether subjects will be randomized and whether subjects will receive any placebo.
- *Community-Based Participatory Research:* If you are conducting [community-based participatory research \(CBPR\)](#), describe strategies for involvement of community members in the design and implementation of the study, and dissemination of results from the study.
- *Qualitative research:* Indicate ranges where flexibility is needed, if a fixed interview transcript is not available, describe interview topics including the most sensitive potential questions.
- *Research Repositories:* If the purpose of this submission is to establish a Research Repository (bank, registry) and the material you plan to collect is already available from a commercial supplier, clinical lab, or established IRB approved research repository, provide scientific justification for establishing an additional repository collecting duplicate material. Describe the repository design and operating procedures. For relevant information to include, see the [UK Research Biospecimen Bank Guidance](#) or the [UK Research Registry Guidance](#).

We will perform a stratified cluster randomized controlled trial with randomization of participating clusters into a "GROUP CARE" or "TELEMEDICINE" arm. Sites will be stratified into "high volume" (>500 deliveries/year) and "low volume" (<500 deliveries/year). Randomization will be 1:1 within each strata. According to 2016 site specific delivery data, 6 sites are "low volume" and 6 sites are "high volume". All enrolled study patients will continue to receive regular prenatal care (PNC) through their community based obstetric

providers and medication assisted treatment (MAT) with buprenorphine or methadone for opioid use disorder (OUD) through their respective licensed prescribing providers. In addition to PNC and MAT, study patients will receive supplementary clinical care every two weeks either in the form of a structured group model (GROUP CARE) or in a telemedicine consult (TELEMEDICINE) for OUD in pregnancy through their allocation into the "group" or "telemedicine" arm of the trial. Half of the participating clusters will be randomized to receive group prenatal care ("group" arm) imparted through a perinatal nurse facilitator and community based peer support specialist. The remaining clusters will receive pregnancy specific education through telemedicine imparted by a Perinatal nurse educator, substance abuse counselor and/or Peer Support Specialists. The supplemental clinical care that patients will consist of a standardized rotating 8 topic patient education curriculum, including the following topics: 1. Treatment Options for Opioid Use Disorder 2. Smoking Cessation 3. Relapse Prevention Education 4. NAS Reduction Education 5. Breast Feeding Support/Education6. Domestic Violence Education 7. Postpartum Depression 8. Birth Control/Family Planning.

Meetings and consultations will occur every two weeks in each arm of the trial from enrollment until 8 weeks post-partum and will then continue monthly until 6 months post-partum.

Potential Perinatal Nurse Facilitators will be identified at each study site randomized to the "group" arm. These individuals will undergo a two-day training program with the UK-PATHways: Hub Perinatal Nurse Facilitator ([name], see key personnel). The UK-PATHways: Hub Perinatal Nurse Facilitator will serve as a point person for study site Nurse Facilitators and lead monthly meetings via Skype or in person. Peer Support Specialists will be identified within the region (three total) and, if not previously certified/trained, training will be provided.

Telemedicine arm consultations will be provided by study personnel identified within this application including [name], LMFT, [name] and [name].

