**SUBJECT DEMOGRAPHICS**

0 unresolved comment(s)

Age level of human subjects: (i.e., 6 mths.; 2yrs., etc.)  to **Study Population:**

Describe the characteristics of the subject population, including age range, gender, ethnic background and health status. Identify the criteria for inclusion and exclusion.

Provide the following information:

- A description of the subject selection criteria and rationale for selection in terms of the scientific objectives and proposed study design;
- A compelling rationale for proposed exclusion of any sex/gender or racial/ethnic group;
- Justification for the inclusion of vulnerable groups such as children, prisoners, adults with impaired consent capacity, or others who may be vulnerable to coercion or undue influence.

Please consider these resources:

[NIH Diversity Policy](#)

[FDA Diversity Guidance](#) 

Pregnant women at 6 to 32 weeks' gestational age with a history of OUD (as defined by the DSM-5) who are receiving MAT (with either buprenorphine based products or methadone) and obtaining prenatal care at one of twelve study sites. Study sites are located throughout Central and Eastern Kentucky and have an established relationship with the University of Kentucky through an existing telemedicine network called the Kentucky Angels network.

Study sites include:

1. Ashland, KY - Karen's Place Maternity Center, ARC
2. Bowling Green, KY: Fairview Community Health Center
3. Corbin, KY: Grace Community Women's Health
4. Georgetown, KY: Brightview Health, LLC
5. Georgetown, KY: UK Women's Health Obstetrics and Gynecology – Georgetown
6. Louisville, KY: University of Louisville, HCCP/Prenatal Clinics
7. Middlesboro, KY: ARH Women's and Family Health Center-Middlesboro
8. Morehead, KY: UK Morehead Women's Healthcare
9. Prestonsburg, KY: Frontier Behavioral Health Center, PLLC
10. South Williamson, KY: ARH Women's and Family Health Center - Tug Valley
11. Vico, KY: Primary Care Centers of Eastern Kentucky
12. Pikeville, KY - Pikeville Medical Center

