## A. Explain why your research does not involve greater than minimal risk:

We are performing no direct medical intervention to the research participants - they will be given no study medications and their prenatal care and/or their substance abuse care will not be altered in any way. They will participate in a prenatal education curriculum which is not anticipated to increase their risk at all. We will collect infant developmental outcome data via maternal questionnaire at 3 and 6 months. There will be no study intervention performed on the neonates.

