## 6 months Post-Partum

- 1) WHO QoL-BRF
- 2) Experience of Care and Health Outcomes (ECHO) - modified
- 3) Cornell Health Services Index (CHSI)
- 4) Fagerstrom nicotine Dependence
- 5) Edinburgh Depression Scale
- 6) GAD-7
- 7) Ages and Stages

Study participants will be asked to complete surveys in REDCap available on iPads dedicated specifically for this project; however, all participants will have the option to complete hard copies of the surveys if they prefer. Data from surveys completed on iPads will be uploaded directly into REDCap. Devices will be managed by UK Healthcare IT, which already deploys a large number of iPad devices and is very familiar with the security and management requirements of iOS based devices. UK Healthcare IT currently has a management app configured to ensure the security of the devices and to apply sufficient restrictions that the devices cannot be used for unintended purposes. All devices will be stored securely in locked cabinets.

We will be collecting the following maternal data:

1. Prenatal labs
2. Infectious complications
3. MAT program participation rate (by patient)
4. Study program participation rate (e.g. frequency of clinic attendance at telemedicine and/or group sessions);
5. Prenatal care attendance (medical record review).
6. Urine drug screen result on admission to labor and delivery, 3 and 6 months postpartum (obtained from medical records)
7. Smoking status: evaluated through patient interview and Fagerstrom Nicotine Dependence Scale at intake, 3rd trimester, 3 and 6 months postpartum.
8. Addiction severity: DSM-5 Criteria for Opioid Use Disorder at intake
9. Obstetric complications including but not limited to Preterm birth <37 GA, growth restriction (<10%ile), preterm rupture of membranes, preeclampsia, multiple gestation, gestational diabetes, chorioamnionitis, miscarriage, fetal demise, cesarean delivery (medical record review)
10. Overdose tracking (overdose reversal agent needed, admitted to hospital/ED for overdose): patient interview at every visit
11. Health services utilization: Cornell Health Service Index administered in 3rd trimester, 3 and 6 months post-partum
12. Patient experience of care: Experience of Care and Health Outcomes (modified) Survey administered in 3rd trimester, 3 and 6 months post-partum
13. Depression: Edinburgh Postpartum Depression Scale administered at intake, 3rd trimester, 3 and 6 months postpartum

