Some of the research materials to be collected includes gestational outcomes data, including but not limited to: details of maternal prenatal care, labor and delivery outcomes, details pertaining to the course of their OUD in pregnancy and details pertaining to individual patient MAT course, as well as neonatal data including hospital course, Finnegan scoring, incident NAS, neonatal treatment and follow up. These will be abstracted from a review of the standardized and template based electronic medical record system. These will be collected and stored in a HIPAA compliant safe and secure environment by personnel specifically trained in the handling of PHI.

Healthcare related data that will be collected will be stored in a secure, password protected electronic file on a single computer workstation with limited access. Similarly, all paper based documentation bearing identifying information will be stored in a secure locked filing cabinet under the PI's supervision. All data will be De-identified by stripping it of all identifiable PHI at the time of collection. Hence the data that will be used for analyses and review will be entirely De-identified, with study participants being referenced only through randomly generated numbers assigned to each study participant. This is being done to ensure the maintenance of confidentiality for the study participants and safety with regard to the use of healthcare data.

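### Adjustment for the opioid agent at enrolment (buprenorphine or methadone) is not prespecified, although it is a plausible prognostic factor for NAS and about six sites per arm cannot be relied on to balance it

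*Combined protocol and SAP*

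**What the plan says.** **Agent.** Subject Demographics admits women "who are receiving MAT (with either buprenorphine based products or methadone". Under Study Design they continue on "medication assisted treatment (MAT) with buprenorphine or methadone for opioid use disorder (OUD) through their respective licensed prescribing providers". The trial does not intervene on this: the minimal-risk statement in the Children section says that "their prenatal care and/or their substance abuse care will not be altered in any way".

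**Allocation.** Sites are the randomised unit. Study Design gives one stratification factor: "Sites will be stratified into 'high volume' (>500 deliveries/year) and 'low volume' (<500 deliveries/year". It adds that "Randomization will be 1:1 within each strata" and that "6 sites are 'low volume' and 6 sites are 'high volume".

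**Analysis.** The SAP plans a generalized linear mixed model that allows for clustering, with a noninferiority analysis of the primary outcome. Its covariates are examples, to be used if required: age, race, socioeconomic status and addiction severity. Addiction severity is measured by DSM-5 criteria at intake, which do not identify the agent. No noninferiority margin is stated, and no analysis by agent is described.

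**Data.** The numbered maternal list under Data Collection & Research Materials itemises "MAT program participation rate (by patient". The Records, Privacy, and Confidentiality section says that "details pertaining to individual patient MAT course" will be abstracted. The recruitment section has the site nurse confirm that MAT is being taken; it does not mention which agent.

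**Aim 2.** Objectives compares each arm with the established hub programme, which is not among the listed study sites.

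**The concern.** NAS is assessed in infants whose mothers took one of two opioid agents during pregnancy, so the agent is an obvious candidate prognostic factor for the primary outcome. It is set outside the trial. If prescribing habits differ between sites, the agent mix varies at the level that was randomised, and one or two sites with an unusual mix can leave the arms unequal. Delivery volume, the only stratifier, need not track prescribing.

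If the agents also differ in NAS risk, the arm contrast then carries part of the agent difference. In a noninferiority comparison a shift in either direction makes the result harder to read. Because covariates enter only as required, whether to adjust could be settled after the imbalance and the outcome are known.

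**Working it through.** The documents contain no sample-size, margin or intraclass-correlation figure, so there is no planned number to reproduce. The check asks how far agent mix alone could move the NAS difference.

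**Inputs from the documents**
- 12 sites, 6 per volume stratum, allocated 1:1 (Study Design), so about 6 per arm. Research Procedures and Resources say 11 sites; both counts were run.
- At most 267 subjects (front page): 267/12 = 22.25, taken as m = 22 per site.

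**Assumed inputs**
- Mean share μ on one agent: 0.30.
- Between-site SD s of that share: 0.15, 0.25 or 0.35.
- NAS risk difference d between agents: 0, 5, 10 or 20 points.
- Sites of equal size, and agent share unrelated to delivery volume.

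**Formulas**
- SD of the arm difference in share = √{(2/6)[s² + (μ(1−μ) − s²)/m]}
- Induced NAS difference = d × arm difference in share

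For s = 0.25: √{(1/3)[0.0625 + (0.21 − 0.0625)/22]} = √0.0231 = 0.152.

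**Results** (20,000 simulated allocations, 12 sites; the last four columns give the half-range in points containing 95% of allocations)

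| s | SD of arm difference in share | Imbalance ≥ 10 points | Imbalance ≥ 20 points | d = 0 | d = 5 | d = 10 | d = 20 |
|---|---|---|---|---|---|---|---|
| 0.15 | 0.102 | 32% | 5% | 0 | 1.0 | 2.0 | 3.9 |
| 0.25 | 0.152 | 50% | 19% | 0 | 1.5 | 3.0 | 5.9 |
| 0.35 | 0.207 | 62% | 34% | 0 | 2.0 | 4.1 | 8.2 |

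With 11 sites the chance of an imbalance of 10 points or more is 35%, 53% or 64%, and the largest half-range is 8.4 points.

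**Scale.** Ignoring clustering, the standard error of the NAS difference with 133.5 women per arm is √(2p(1−p)/133.5): 5.6 points at a NAS rate of 30% and 6.1 at 50% (rates assumed). The SD of the agent-induced shift runs from 0.102 × 5 = 0.5 points to 0.207 × 20 = 4.1 points when d is not zero.

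**Cost in precision.** Between-site variation in agent adds an intraclass correlation of (d × s)²/[p(1−p)]. At an assumed NAS rate of 40% the added design effect is 21 times this:
- d = 5 points, s = 0.15: ICC 0.0002, design effect +0.005, standard error × √1.005 (about 0.2% larger).
- d = 10 points, s = 0.25: ICC 0.0026, design effect +0.055, standard error × √1.055 (about 3% larger).
- d = 20 points, s = 0.35: ICC 0.0204, design effect +0.43, standard error × √1.43 (about 20% larger).

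**The case against.** The strongest reply is that this is chance, not bias. Sites are randomised, so any effect of agent mix on the arm contrast is symmetric about zero. A site random effect carries the between-site variation into the standard error, so the interval already allows for most of it. That stands for the randomised comparison, provided inference uses degrees of freedom suited to about 12 sites, which the SAP does not specify. A reader might infer that the NAS comparison is confounded by site prescribing; the documents do not support that. Enrolment after site allocation could make the agent mix depend on arm, but nothing shows that it does.

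Three further points stand:
- **Premises.** No passage says that NAS risk differs between the agents, or that agent choice clusters by site. Women have their own prescribers, and MAT need not be prescribed where prenatal care is given. With equal risks the shift is zero.
- **Control.** It is tempting to say that the agent is uncontrolled or unrecorded. The covariate list is open, so adjustment is not excluded, and MAT course details are to be abstracted. What is missing is prespecification and an explicit field.
- **Screening.** It is also tempting to say that the agent is already checked at screening. The recruitment text covers only whether MAT is taken.

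The reply does not remove the case for adjustment. A random effect widens the interval but does not correct the realised contrast, whereas a prognostic baseline covariate helps with both. It also gives no protection to the Aim 2 comparison with the hub.

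**Conclusion.** The point holds as a missing prespecification with a cheap remedy. The agent at enrolment is a plausible prognostic factor for NAS, is not a stratifier, and is not among the named covariates. If prescribing differs by site, an imbalance of 10 points or more in agent share would arise in about a third to two thirds of allocations under the assumed SDs.

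The effect on the NAS difference depends on a risk difference that the documents do not give. The 95% half-range is 0 points if the risks are equal, 1 to 2 points for a 5-point difference, 2 to 4 for 10 points and 4 to 8 for 20 points. For the randomised comparison this is lost precision and a less clear noninferiority result. Since no margin is stated, it cannot be said how often the conclusion would change. The Aim 2 comparison is more exposed, because a difference in agent mix between the hub and the trial sites would not be chance imbalance.

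**What to change.** 1. Record the MAT agent at enrolment as an explicit REDCap field. The planned abstraction of the MAT course suggests that it can be obtained.
2. In the SAP, name enrolment agent (buprenorphine or methadone) as a fixed covariate in the primary NAS model, whatever the observed imbalance.
3. Tabulate agent by arm and by site. An Aim 2 comparison would need the same field for the hub women.
4. Report the arm contrast as a covariate-standardised risk difference: predict each woman's NAS risk under each arm, average over the observed covariates and the site effect, and subtract. Under a logit link, adding a prognostic covariate changes the odds ratio being estimated; standardising keeps the noninferiority comparison on one scale.
5. Describe agent and dose after enrolment by arm, but do not adjust for them in the primary analysis. The curriculum covers treatment options and relapse prevention, so later changes may be effects of the intervention.

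The cost is one data field, one model term and a standardisation step, with no change to patient care. If the agent hardly varies within sites, the term uses about one of the 12 − 2 = 10 between-site degrees of freedom.
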